17.0 Data Management

17.1 Data Analysis Plan:

Descriptive analyses will be computed to determine the usability and acceptability of the delivery formats. We will examine family demographics, included age and gender of parent(s) and child(ren), as well as family structure. We will also compute descriptive analyses on the recruitment data, including the number and percentage of families expressing interest in the study, time to recruit families, the percentage of families screened who meet inclusion criteria. We will also examine retention data including weekly attendance, participants completing home practice assignments, as well as their reasons for absences or drop out.

Complex long-term follow up analyses will also be computed. We will employ standard normal theory pre-post Analysis of Variance and

PROTOCOL TITLE: Comparing Web, Group, and Telehealth Formats of a Military

Parenting Program

VERSION DATE: May 4, 2018

structural equation modeling (SEM) growth curve analyses. For the immediate prepost analyses we will conduct a 3 group by 2 repeated measures Analysis of Variance for parenting, child, and couple functioning constructs focusing on the comparison of change across the Group Based, Individualized Facilitated, and Self-directed ADAPT conditions.

For the intent to treat (ITT) analyses of long term follow up, we will specify latent growth models (LGM) recommended for long term effectiveness designs [110] involving maximum likelihood SEM. Fixed effects (e.g., random assignment to ADAPT, parent and child gender) and time varying random effects may be estimated using chronometric time weights. A model specifying an initial status latent variable (assessing variance in BL differences) and a linear slope latent variable (estimating individual differences in change over time), would be specified using factor weights of 1, 1, 1, 1, for the respective repeated measures, and factor weights of 0, 1, 2, and 4 for growth. The first step in LGM is to identify the model that best characterizes patterns of growth. We can also specify an additional nonlinear quadratic factor, a higher order polynomial function to capture any nonlinearity. Accelerated or decelerated change would be specified with loadings fixed at 0, 1, 4, and 16. A sequential set of models tests the latent variances and model fit across a random intercept, linear growth, and quadratic model to determine the optimal growth pattern [113].

17.2 Power Analysis:

sing an alpha level of .05 and considering 5% attrition over the first 6 months, a pre-post design with 3 groups of 114, within subject SD = 1, and between groups SD = .71; the study is powered .81 to minimally detect a small group by time interaction effect (ES = .12), small time effect (ES = .15), and small group effect (ES = .21) for given parenting, child, couple or parent constructs.

17.3 Data Integrity:

Site coordinators and the project manager will oversee assessment technicians and conduct quality control checks regularly throughout the data collection process. If needed, additional training will be provided to assessment technicians. Video recordings of family interaction tasks will be monitored by the coding coordinator to ensure high quality and consistency across assessment technicians. Survey data will be cross-checked and cleaned shortly after in-home assessments are conducted to ensure data were collected accurately as well as resolve any discrepancies in key study variables (e.g., deployment status, marital status, gender, etc).

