VERSION DATE: May 4, 2018

Analysis of Aim 1: ADAPT comparative effectiveness hypotheses will be tested using standard normal theory Analysis of Variance and multiple regression techniques in structural equation modeling (SEM) with a focus on growth curve analyses for follow up data. We will specify analyses to test Hypothesis 1: NGR families in both the ADAPT group-based condition and the ADAPT web-facilitated condition will show greater pre-post improvements in observed parenting, and parent, child, and couple functioning relative to the self-directed web condition; and Hypothesis 2: ADAPT group-based condition will be equally effective as the individualized ADAPT web-facilitated condition.

Analyses for Hypothesis 1 of Aim 1. We will employ standard normal theory pre-post Analysis of Variance and structural equation modeling (SEM) growth curve analyses for the long-term follow up. For the immediate pre-post analyses we will conduct a 3 group by 2 repeated measures Analysis of Variance for parenting, child, and couple functioning constructs focusing on the comparison of change across the Group Based, Individualized Facilitated, and Self-directed ADAPT conditions. The study randomly allocates 360 NGR families across the three conditions ($n = 120$ per group). For the 6-month assessment, we estimate a projected 5% attrition rate and over the 24-month follow up we expect roughly 15% attrition. In two prior PMTO randomized trials with intensive multiple-method family assessments, family retention was 88% and 86%, respectively, at 30-month follow-ups [2, 12]. In both of those studies, there were no differential rates of attrition between intervention and controls, there was less than 5% attrition by the immediate 6 month post-test assessment, and less than 15% attrition by the 24 month assessment. Using an alpha level of .05 and considering 5% attrition over the first 6 months, a pre-post design with 3 groups of 114, within subject $SD = 1$, and between groups $SD = .71$; the study is powered .81 to minimally detect a small group by time interaction effect ($ES = .12$), small time effect ($ES = .15$), and small group effect ($ES = .21$) for given parenting, child, couple or parent constructs.

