identify the model that best characterizes patterns of growth. We can also specify an additional nonlinear quadratic factor, a higher order polynomial function to capture any nonlinearity. Accelerated or decelerated change would be specified with loadings fixed at 0, 1, 4, and 16. A sequential set of models tests the latent variances and model fit across a random intercept, linear growth, and quadratic model to determine the optimal growth pattern. The comparative effectiveness hypothesis for observed parenting is shown in Figure 2 as linear growth. Group Based and Web Facilitated will be contrasted to the Self-Directed omitted group. Analyses will test that the Group Based effect ($\beta_1 > 0$) and the Web Facilitated ($\beta_2 > 0$) will show greater 2-year improvements relative to Self-Directed. For the LGM in Figure 2 we estimated power using Mplus Monte Carlo simulations with 1000 replications. An advantage of this approach is the ability to incorporate specific patterns of expected attrition over time. For the figure in Figure 3, contrasts for Group Based and Web Facilitated were fixed at a mean of .33 and variance of .22 representing the random allocation across groups. The latent initial status intercept and latent growth factors were specified reflecting a commonly observed ratio of 5:1 for the variance components (Initial Status $\psi_2 = .5$ and SD = .70; and Linear Growth $\psi_2 = .1$, SD = .31). The effect size (ES) is then the ratio of group contrast mean differences in the latent growth factor divided by the SD for growth. A sample size of 306 (cumulative attrition of 15% over 2 years, specified as .05, .10 and .15 over time) obtained power of .98 respectively to detect small effects (ES=.10) for β_1 and β_2 relative to Self-Directed and likewise for child, couple, parent adjustment.

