PROTOCOL TITLE: Comparing Web, Group, and Telehealth Formats of a Military Parenting Program

VERSION DATE: May 4, 2018

be completed during the baseline or follow-up, or study staff will provide funds for the family to travel to a local library, University, etc. to gain computer access.

Sources of Materials

- Research material obtained from human subjects will consist of data collected specifically for this study.

The data will include:

1. Web-based questionnaires filled out by families
2. Observational coding data based on videotaped parent-child interaction tasks completed by families
3. Short questionnaire packets filled out by families and teachers
4. Short surveys and web conference calls completed by expert panel members.
5. Audio and video tape of parent's response to KidVid (video of parenting tasks)

Measures and Assessments:

There are 4 assessments: Time 1- baseline (BL, prior to start of the intervention), Time 2 - six months post BL (post-intervention, given 4-5 month intervention at 3 sessions/month, allowing for holidays, etc), Time 3- 12 months following BL, and Time 4, 24 months after BL. Assessments are weighted to be gathered in the first year, (BL, 6, and 12 months) to gauge intervention effects immediately at posttest (i.e., T2) and at T3, which is when parenting and teacher report outcomes indicated change in prior studies. All measures (i.e., child, parent, and teacher report, and direct observations) will be gathered annually (T1, T3, T4), ensuring that teachers are different at each assessment. At T2, only parent report data will be gathered, online, (no in-home assessment) to minimize participant burden in Year 1, and because in prior studies observed parenting and teacher report outcomes indicated change at 12 months, while parent report indicated some change immediately posttest. Child self-report measures will be gathered (and were standardized with) children over age 8. Measures are summarized below:

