Child adjustment and substance use. Child adjustment will be assessed with the Behavioral Assessment Scale for Children (BASC-2; teacher, parent, and child self-report, a system assessing broad domains of externalizing problems, internalizing problems, and adaptive skills. Items are rated on a 4-point scale. Gender-specific normative scores are provided in the form of T-scores. Parents use the parent version of the BASC2 (BASC2-PRS; alphas = .80-.87); teachers use the Teacher Report Form (BASC2-TRS; alphas = .85-.89). Child intentions and use of substances will be assessed using self-report for children in 5th grade and up, given sensitivity of questions, and given data suggesting that some children begin experimenting with substances at this age: in a study of 2300 students, 16.1% of 5th graders, and 29.4% of 6th graders reported ever having used alcohol. Tobacco use will be assessed with 6 items reflecting tobacco use behavior (ever taken a puff, smoked a whole cigarette, current smoking, $\alpha=.84$) and intentions to smoke; $\alpha=.78$ [17]. Alcohol Use Intentions and Behavior Scale. This 9-item scale measures alcohol use in the past year, month, week, heavy drinking (5+ drinks in past 2 weeks), ever having been drunk, and intentions to drink if offered by a friend, in the next month, in high school and as an adult (scale range 9-49; $\alpha=.82$). The combined scale and two subscales (Alcohol Use Behavior and Alcohol Use Intentions) have adequate internal consistency and test-retest reliability. Child distress will be measured using the Children's Depression Inventory [19], a 27-item symptom-oriented summative index (e.g., "I am sad," "nobody loves me") that has been repeatedly shown to correlate highly with similar measures of depression and to distinguish between clinical and non-clinical samples. Since the CDI is designed to be sensitive to change over time, test-retest reliability varies between .38 and .87 depending on the sample and the time interval being used. PTSD Reaction Index is a 20-item child interview assessing posttraumatic stress reactions; the child is asked to endorse how frequently each reaction occurs on a four-point scale. Scores are strongly associated with diagnostic measures of PTSD. Child peer adjustment will be measured using a 16-item scale assessing loneliness and dissatisfaction with peer relations. Items include "I have nobody to talk to," "I don't have any friends," and "It's hard to get other kids to like me." The Describing Friends is a measure of deviant peer association – a summative index of five items scored true or false. Items are child reports of friends' deviant behavior (e.g., my friends get into fights, clown around, get into trouble, do not like schoolwork, find schoolwork too hard). Childhood exposure to stressful and traumatic events will be collected using the Children Lifetime Events questionnaire previously and successfully used in the original ADAPT study. These questions will be collected at T4 only.

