9.0 Study Population

9.1 Inclusion Criteria:

Inclusion criteria are: (a) one parent has returned from deployment to OIF or OEF or stateside deployment in support of the Global War On Terrorism, (b) at least one child ages 5-12 in their custody and living with parent(s) in the home, and (c) high speed internet access at home (a MN study indicates that 97% deployed families have internet, with 70% using internet daily; Sayer et al., 2009). We will include both single-and two-parent families, as well as families where care is shared between non-partnered adults (e.g. grandparent and mother), and will control for relationship status in analyses. Participants must live within an hour's

PROTOCOL TITLE: Comparing Web, Group, and Telehealth Formats of a Military

Parenting Program

VERSION DATE: May 4, 2018

travel time of Grand Rapids, Kalamazoo, Battle Creek or Selfridge, MI, the Twin Cities Metro area, St. Cloud or Duluth, MN, agree to randomization, and indicate willingness to interact with study materials and complete assessment batteries.

9.2 Exclusion Criteria:

Exclusion criteria include: (a) active psychosis, (b) an open child protection case for abuse or neglect in the family, (c) a serious child mental health diagnosis, (d) families who piloted material or participated in or are currently participating in the original ADAPT RCT. MN ARNG data indicate that fewer than 10% families would be excluded based on a-c, above (personal correspondence, [name]).

There is no reason to exclude women of childbearing potential. There will be no exclusion of racial or ethnic groups.

9.3 Screening:

Potential participants will be asked to take an online eligibility survey that will screen for inclusion criteria.

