DADS Loneliness & Social Dissatisfaction Scale (LONE) administered to children between 4-7	24		x			N/A		x	
DADS Loneliness & Social Dissatisfaction Scale-Y (LONE-Y) administered to children 8 and older	24		x			N/A		x	
Child Depression Inventory – short version (CDI) administered to children 7 and older	10		x			N/A		x	
DADS Describing Friends (DESS) - administered to children between 4-7	25		x			N/A		x	
DADS Describing Friends (DESS) – administered to children 8 and older	44		x			N/A		x	
Behavioral Assessment System for Children – 2 (BASC) – SRP-I (administered to children 5-7)	65		x			N/A		x	
Behavioral Assessment System for Children – 2 (BASC) – SRP-C (administered to children 8-11)	139		x			N/A		x	
Behavioral Assessment System for Children – 2 (BASC) – SRP-A (administered to children 12 and older)	176		x			N/A		x	
The American Drug and Alcohol Survey (ADAS) & 8 supplemental questions (administered to children 10+)	88		x			N/A		x	
Wechsler Abbreviated Scale of Intelligence – 2 (WASI-2) – vocabulary and matrix reasoning only	61		x			N/A			
Family Interaction Tasks	N/A		x			N/A		x	
	Items	T1		T2		T3		T4	
		OL	IH	OL	IH	OL	IH	OL	IH
Measures - Teacher									
Behavioral Assessment System for Children – 2 (BASC) PRS-P (administered to teachers of kids age 5)	100	x				N/A	x		x
Behavioral Assessment System for Children – 2 (BASC) – TRS-C (administered to teachers of kids age 6-11)	139	x				N/A	x		x
Behavioral Assessment System for Children – 2 (BASC) – TRS-A (administered to teachers of kids age 12+)	139	x				N/A	x		x

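### The stated power for couple outcomes counts every retained family, although families without a couple are enrolled; for child outcomes only the growth-model claim for age-limited self-report is affected

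*Protocol*

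**What the plan says.** Section 17.2, repeated in section 1.1 (Analyses for Hypothesis 1 of Aim 1), sets power for the baseline-to-6-month analysis at an "alpha level of .05 and considering 5% attrition over the first 6 months". It uses three groups of 114 and claims .81 for a group-by-time effect of .12, "for given parenting, child, couple or parent constructs". Section 1.1 (Follow Up Analyses) claims .98 for an effect of .10 in the latent growth model with 306 families, and "likewise for child, couple, parent adjustment".

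On who can supply these outcomes:

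- Section 9.1: "We will include both single-and two-parent families", together with families in which unpartnered adults share care. Relationship status is to be controlled for in the analyses. No expected share is given.
- ADAPT4U Measures table: the couple measure is the seven-item Dyadic Adjustment Scale (DAS-7), completed by parents at all four time points.
- Sections 5.2 and 5.3: "Child self-report measures will be gathered (and were standardized with) children over age 8". At 6 months only parent report is collected.
- Section 5.2: substance use is assessed "using self-report for children in 5th grade and up".
- ADAPT4U Measures table: the child depression inventory (CDI) starts at age 7 and the drug and alcohol survey at age 10. There are also self-report forms for younger children, such as the BASC "SRP-I (administered to children 5-7" and loneliness and friends measures for ages 4 to 7.

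**The concern.** Both sample sizes come from all randomised families with a deduction for attrition and nothing else. Couple functioning is a named outcome of Hypothesis 1 and of the pre-post analysis of variance, yet some enrolled families have no couple to rate. Controlling for relationship status cannot supply an outcome that does not exist. Some child self-report is likewise limited to part of the enrolled age range of 5 to 12.

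The pre-post claim has almost no slack, so a small loss takes it below .80. A null couple result would then be read as coming from a better-powered comparison than was run. The same holds to a lesser degree for a null long-term result on an age-limited child measure.

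**Working it through.** **Inputs from the protocol.** "The study randomly allocates 360 NGR families across the three conditions" (120 per arm). Alpha .05; interaction effect f = .12; 5% attrition at 6 months and 15% at 24 months; stated power .81 and .98.

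**Sample sizes.** 360 × .95 = 342 = 3 × 114. 360 × .85 = 306. No other deduction is made.

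**Reproducing .81.** The group-by-time test is an F test on 2 and N − 3 degrees of freedom. With noncentrality λ = 2·N·f² = 2 × 342 × .0144 = 9.85, power is .806, which matches. The protocol does not state its convention. λ = N·f²/.71² gives .802, while λ = N·f² gives .494 and does not match. The first is used below.

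**Couple outcomes, pre-post.** Let s be the share of families with a couple score, so N = 342·s. The shares are assumptions.

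| Non-partnered share | N | λ | Power at f = .12 |
|---|---|---|---|
| 0% | 342 | 9.85 | .806 |
| 5% | 325 | 9.36 | .784 |
| 10% | 308 | 8.86 | .760 |
| 20% | 274 | 7.88 | .705 |
| 30% | 239 | 6.89 | .642 |

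The effect detectable with .81 power rises from .121 to about .127, .135 and .144 at 10%, 20% and 30%.

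**Couple outcomes, growth model.** The simulation behind .98 cannot be rerun from the text, so the stated figure is taken as given and scaled by the square root of the sample size, two-sided at .05: power = Φ[(2.054 + 1.960)·√s − 1.960].

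- s = .95: 4.014 × .975 − 1.960 = 1.95, power about .975
- s = .90: 4.014 × .949 − 1.960 = 1.85, power about .97
- s = .80: 4.014 × .894 − 1.960 = 1.63, power about .95
- s = .70: 4.014 × .837 − 1.960 = 1.40, power about .92

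**Child outcomes, pre-post.** No child self-report is collected at 6 months. The child measure then is the parent-report BASC, with forms for age 5, ages 6–11 and age 12 and over. Every enrolled age is covered, so N stays at 342 and power at .81.

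**Child outcomes, growth model.** Assume baseline ages uniform over the eight years 5 to 12, and apply the same scaling.

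- CDI from age 7: 6/8 = .75, power about .94
- Substance use from age 10, taken as roughly 5th grade: 3/8 = .375, power about .69

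These are lower bounds, because children age into the measures. On the same assumption, at 24 months all are 7 or older and 5/8 are 10 or older.

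**Text against table.** Sections 5.2 and 5.3 confine child self-report to children over 8; the table lists forms for ages 4–7 and 5–7. If the text governed, ages 9–12 would supply 4/8 of children at baseline and the .98 would scale to about .81 for child self-report generally. If the table governs, BASC self-report covers the whole range and loses nothing. The analysable number depends on which applies.

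**The case against.** The best reply is that nothing has been miscalculated and that the couple point rests on an inference. Both observations are fair. The .81 is correct for 342 families. No passage says that single parents skip the DAS-7; the table lists it without restriction, although it marks other measures as restricted. A single parent might also have a partner outside the home. The inference from a dyadic scale is nonetheless a safe one, and the protocol neither defines a couple score for an unpartnered parent nor reduces the number for this reason. That the growth model uses maximum likelihood does not help either: a family with no couple score at any time point says nothing about change in couple functioning.

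It is also fair that the size is unknown. At 5% to 10% non-partnered the loss is small, and the growth-model figure for couples stays above .90 even at 30%.

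A reader might go further and infer that child power at 6 months also collapses, to roughly a half or less, because only older children self-report. The protocol does not support this, since no child self-report enters that analysis. Nor does it support saying that all child outcomes are underpowered at 24 months: parent- and teacher-report BASC cover every age, and so does BASC self-report in the table. It is also open whether the growth-model sentence covers substance use at all. It speaks of child adjustment, and section 5.2 names substance use alongside adjustment rather than within it.

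**Conclusion.** The point holds for couple outcomes, and the pre-post claim is the one that matters. The stated .81 needs every retained family to have a couple score; a non-partnered share of only 5% takes it to about .78, and 20% to about .71. These figures assume that non-partnered families supply no couple score, that they are spread evenly over the arms, and that attrition is the same for both family types. The protocol does not give the share, so it cannot be said that the couple sample is far below 114 per arm, only that it is below it.

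For child outcomes the 6-month power stands. The .98 growth-model claim is overstated only for age-limited self-report, by an amount bounded by the figures above. The conflict between text and table on child self-report ages is real in its own right.

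**What to change.** 1. In sections 1.1 and 17.2, restate couple power on the expected number of partnered families, for both the pre-post and the growth-model analyses. State the assumed share and show a range around it.
2. In section 1.1 (Follow Up Analyses), limit the child power statement to measures collected on all children, or give the expected number and power for each age-limited measure. Say whether the statement covers substance use.
3. Reconcile the over-8 rule in sections 5.2 and 5.3 with the self-report forms for ages 4–7 and 5–7 in the ADAPT4U Measures table.

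No families need be added. The cost is a less favourable stated power for couple outcomes and for age-limited child measures.
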